6.3. Vital Signs and Physical Examination Findings

Continuous vital sign variables including weight, waist circumference, temperature, supine and standing pulse, supine and standing blood pressure (systolic and diastolic), and BMI will be summarized at each assessment time point by treatment group. BMI will be calculated as weight (kg)/(height (m))², at each time point that body weight is measured. The height measurement collected at screening will be used in the calculation. Changes from baseline to each postbaseline time point will be summarized. Descriptive statistics (N, mean, SD, median, minimum and maximum) will be presented.

Incidence of treatment-emergent clinically important abnormalities in vital signs during the double-blind phase, as defined in Table 6, will be summarized for subjects who had at least one postbaseline assessment for that vital sign. If the baseline value is missing, the postbaseline value will be compared against the abnormally low/abnormally high criteria. Vital sign assessments collected during follow-up will not be used for this summary.

Table 6: Clinically Important Abnormalities in Vital Signs

Vital Sign Parameter	Postbaseline value outside of normal limit if:
----------------------	--

	Abnormally low	Abnormally high
Pulse (bpm)	A decrease from baseline of ≥ 15 to a value ≤ 50	An increase from baseline of ≥ 15 to a value ≥ 100
Systolic BP (mmHg)	A decrease from baseline of ≥ 20 to a value ≤ 90	An increase from baseline of ≥ 20 to a value ≥ 180
Diastolic BP (mmHg)	A decrease from baseline of ≥ 15 to a value ≤ 50	An increase from baseline of ≥ 15 to a value ≥ 105
Body weight (kg)	A decrease from baseline of $\geq 7\%$	An increase from baseline of $\geq 7\%$
Body temperature ($^{\circ}\text{C}$)	$< 35.5^{\circ}\text{C}$	$> 37.5^{\circ}\text{C}$

BP = blood pressure

A listing of subjects with treatment-emergent clinically important abnormalities in vital signs will be presented.

Orthostatic hypotension is defined as an absolute decrease in systolic (>20 mm Hg) or diastolic (>10 mm Hg) blood pressure after standing for at least 1 minute relative to supine position with an increase in pulse rate of >15 beats per minute (Table 7). The number and percentage of subjects who experience treatment-emergent orthostatic hypotension outside of predefined limits at any time during the double-blind phase and for whom the orthostatic hypotension was not present at baseline will be tabulated. Vital sign assessments collected during follow-up will not be used for this summary.

Table 7: Abnormal Limits for Orthostatic Hypotension Parameters (Changes in Vital Signs in Standing Relative to Supine Position)

Vital Sign	Outside of normal limit if difference (standing minus supine)
(1) Pulse (bpm)	> 15 bpm
(2a) Systolic blood pressure (mm Hg) (SBP)	< -20 mm Hg
(2b) Diastolic blood pressure (mm Hg) (DBP)	< -10 mm Hg

Note: Orthostatic hypotension requires that conditions (1) and [(2a) or (2b)] are met.

For subjects who are unable to stand and have the vital signs measured in a sitting or supine position instead of the standing position, the difference between standing and supine values will remain missing.

A listing of subjects with treatment-emergent orthostatic hypotension will be presented.

In addition, a by-subject listing of the physical examination data will be presented.

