## 1.2. Comparator Drug

### Quetiapine Fumarate Extended-release Tablets

Quetiapine extended-release (XR) will be included in this study as an active comparator to investigate potential differentiating features between JNJ-42847922 and quetiapine XR in the augmentation of selective serotonin reuptake inhibitor (SSRI)/serotonin-norepinephrine reuptake inhibitor (SNRI) treatment of MDD.

Quetiapine is a combined dopamine type 2 (D2) and serotonin type 2A (5HT2A) antagonist that belongs to the atypical antipsychotic class. Well-known class effects include neuroleptic malignant syndrome (NMS), somnolence/sedation, metabolic changes (eg, hyperglycemia, dyslipidemia, and weight gain), extrapyramidal symptoms (EPS) including tardive dyskinesia, orthostatic hypotension, and hematologic effects (eg, neutropenia and agranulocytosis), QT prolongation, seizures, and hyperprolactinemia. Additionally, cataract development has been observed in dogs after quetiapine exposure during chronic toxicity studies.

Although the immediate-release formulation was initially approved for use in schizophrenia, quetiapine XR has been shown to be effective for bipolar disorder and as adjunctive treatment with antidepressants for MDD. It is approved in the US and EU for the adjunctive treatment of MDD based on well-controlled studies.

For further information regarding quetiapine XR (including list of adverse reactions, dosage and administration, warnings and precautions, etc) refer to the local prescribing information.

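### The SAP's only table and listing of postural change omit any blood-pressure fall on standing that comes with a pulse rise of 15 bpm or less; a blood-pressure-only row should stand beside the composite

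*SAP*

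**What the plan says.** SAP section 6.3 gives the definition in text and again in Table 7, and the two agree. The text begins "Orthostatic hypotension is defined as an absolute decrease in systolic (>20 mm Hg) or diastolic (>10 mm Hg) blood pressure after standing for at least" one minute relative to supine, and adds "with an increase in pulse rate of >15 beats per minute". Table 7 numbers the pulse condition (1), the systolic condition (2a) and the diastolic condition (2b). Its note joins them: "Note: Orthostatic hypotension requires that conditions (1) and [(2a) or (2b)] are met".

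Two outputs use this definition. One is a count and percentage of subjects who meet it at any time in the double-blind phase and did not have it at baseline. The other is a listing: "A listing of subjects with treatment-emergent orthostatic hypotension will be presented".

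The remaining blood-pressure outputs in section 6.3 are of other kinds. The continuous summaries take the positions separately: "supine and standing pulse, supine and standing blood pressure (systolic and diastolic), and BMI will be summarized at each assessment time point by treatment group". Table 6 sets limits for change from the baseline visit together with an absolute threshold. For low systolic pressure the limit is "A decrease from baseline of ≥ 20 to a value ≤ 90".

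The protocol has no analysis definition of orthostatic hypotension. Section 1.2 includes it among the comparator's well-known class effects ("orthostatic hypotension, and hematologic effects"). Section 9.7 requires supine and standing pressure and pulse, with standing readings after at least a full minute. The Time and Events Schedule places vital signs at every clinic visit.

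**The concern.** The pulse condition acts as a gate. If it fails, the size of the pressure fall is irrelevant. A subject with a very large postural fall and a pulse rise of 15 bpm or less is then indistinguishable, in this table and listing, from a subject with no fall.

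What is at stake is one comparative safety result. The stated purpose of the study (protocol section 11.2, SAP section 1.4) is to look for features that separate the two treatments, and comparative safety, including vital signs, is a secondary objective. A postural effect on blood pressure is one of the features the protocol itself attributes to the comparator. A reader of the study report would have no count by arm of subjects whose pressure fell on standing, only a count of those whose pressure fell and whose pulse also rose past the limit.

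**Working it through.** There is no power or sample-size figure to reproduce here. The check is on what the rule does.

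**1. The rule applied to test cases.** All changes are standing minus supine.

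- SAP rule: event if pulse change > 15 and (systolic change < -20 or diastolic change < -10).
- Blood-pressure criteria alone: systolic change < -20 or diastolic change < -10.

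| Pulse (bpm) | Systolic (mm Hg) | Diastolic (mm Hg) | SAP rule | (2a) or (2b) alone |
|---|---|---|---|---|
| +16 | -21 | 0 | event | met |
| +20 | -5 | -11 | event | met |
| +15 | -21 | 0 | no event | met |
| +15 | -40 | -20 | no event | met |
| +5 | -40 | -20 | no event | met |
| 0 | -60 | -30 | no event | met |
| +30 | -20 | -10 | no event | not met |

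No fall, however large, is counted once the pulse rise is 15 bpm or less.

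**2. Whether another output counts it.**

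- Table 6 needs a fall from baseline of at least 20 and a systolic value of 90 or lower, and does not state body position. From 140 to 92 the change is 48, but 92 is above 90, so it is not flagged. From 110 to 90 the change is 20 and the value is 90, so it is flagged. The comparison is with an earlier visit and not with the supine reading.
- From the continuous summaries a reader can subtract mean supine from mean standing pressure by arm. That gives an average change, not a number of subjects beyond a limit.
- Adverse-event tables contain a postural fall only if the investigator reports one.

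**3. The baseline exclusion.** Suppose a baseline visit shows -25 mm Hg systolic with +10 bpm, and a later visit -40 with +20.

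- Composite: absent at baseline (10 is not above 15) and present later, so a new event.
- Blood pressure alone: already present at baseline (25 is above 20), so excluded.

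The blood-pressure-only count is therefore not simply the composite plus extra cases. Each definition adds some subjects and drops others.

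**4. Size.** Let n be subjects per arm, p the proportion meeting (2a) or (2b), and f the share of those who also exceed +15 bpm. Ignoring the baseline exclusion, the composite counts n × p × f. The SAP plans n = 50. The documents give neither p nor f, so both are assumptions:

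| p (assumed) | Meeting (2a) or (2b), 50 × p | Composite count, f = 0.2 to 0.8 (assumed) |
|---|---|---|
| 10% | 5 | 1 to 4 |
| 20% | 10 | 2 to 8 |
| 30% | 15 | 3 to 12 |

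The spread shows that the number missed is undetermined; it is not an estimate.

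**The case against.** The strongest reply is that nothing is wrong with the definition. Text, table and note agree, and no protocol passage asks for anything else. A composite with a pulse condition is more specific, and replacing it would be a preference. This stands, and is why the composite should be kept.

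It is also fair to say that the missed falls are not invisible. They may be reported as adverse events, they enter the standing and supine summaries, and a low standing value may meet Table 6. That too stands, although none of these routes yields a count of postural falls.

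A reader might infer more: that the rule undercounts in both arms and shrinks the between-arm difference. The documents do not support this.

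- Because of the baseline exclusion (step 3), a wider definition removes some cases as well as adding others, so the net change per arm is unknown.
- The effect on the difference depends on whether f is equal in the two arms. Take an assumed 10/50 against 4/50, a difference of 12 points. With f = 0.2 in both arms the counts are 2 and 0.8, or 1.2/50 = 2.4 points. With f = 0.6 they are 6 and 2.4, or 3.6/50 = 7.2 points. The ratio stays at 2.5 in both cases.
- With f = 0.8 in the first arm and 0.2 in the second, the counts are 8 and 0.8, or 7.2/50 = 14.4 points, which is wider than 12. With the shares exchanged they are 2 and 3.2, a difference of -2.4 points. No passage gives f for either drug.

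A reader might also infer that subjects up to the age limit of 70 are especially likely to be missed because of a weak pulse response. Neither document says so, and the eligibility criteria require subjects to be otherwise healthy and exclude significant or unstable cardiovascular and neurologic disorders.

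Finally, orthostatic hypotension is not an adverse event of special interest, and the table is descriptive in an exploratory study. That limits the importance of the point but does not remove it.

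**Conclusion.** The point holds as a minor gap in reporting, not as an error. Under SAP section 6.3 a postural blood-pressure fall of any size with a pulse rise of 15 bpm or less is absent from the only tabulation and listing of postural change, and no other planned output counts such falls. This follows from the wording of the rule and needs no assumption.

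How many subjects are affected, and which way the between-arm comparison would move, cannot be derived from the documents. The figures above are illustrations under assumed incidences and shares. The primary endpoint and the efficacy analyses are untouched. The case for acting is that the protocol links this effect to the comparator, that the readings are already collected at every clinic visit, and that the change is small.

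**What to change.** In SAP section 6.3 and Table 7:

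- Keep the composite definition and its row as they are.
- Add a row by treatment group for treatment-emergent postural blood-pressure fall, defined as (2a) or (2b) regardless of pulse, in the double-blind phase.
- Apply each definition to its own baseline exclusion. State that the two rows need not nest, since a subject can be a new case under the composite and already present at baseline under the blood-pressure criteria.
- In the listing, include subjects meeting either definition, with a flag for each.

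No new measurement or visit is needed. The cost is one table row, a longer listing and a second count that is less specific than the first. Showing both lets the reader judge how much the pulse condition matters in each arm.

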6.4. Electrocardiogram

Twelve-lead ECGs will be recorded in a supine position so that the different ECG intervals (RR, PR, QRS, QT) can be measured. ECGs will be assessed at screening, Baseline, Week 6, and

Week 24. The ECGs will be read by a central reader. The ECG parameters that will be analyzed are heart rate, PR interval, RR interval, QRS interval, QT interval, and QTc using the following correction methods: Bazett's formula (QTcB) and Fridericia's formula (QTcF).

$$\text{Bazett's formula: QTcB (msec)} = \text{QT (msec)} * (\text{HR(bpm)}/60)^{1/2}$$

$$\text{Fridericia's formula: QTcF (msec)} = \text{QT (msec)} * (\text{HR(bpm)}/60)^{1/3}$$

Descriptive statistics for observed values and changes from average predose will be presented by treatment group for the above ECG parameters at each scheduled time point. Average predose ECG is defined as the average of all ECG results collected up to and including the day of the first dose of study drug.

The identification of treatment-emergent abnormal ECG values is based on the post-baseline value (a value occurring after the first study drug administration) being out of range while the average predose value is either missing or within the limits given in Table 8. If post-baseline ECG results are above the upper limits (abnormally high) and the average predose value is below the lower limits (abnormally low), then the post-baseline abnormality will also be considered treatment-emergent. The same applies to the post-baseline value being below the lower limits (abnormally low) with the average predose value being above the upper limits (abnormally high). The number and percentage of subjects with treatment-emergent ECG values outside the pre-defined normal limits defined below will be presented by treatment group.

Table 8: Abnormal Limits for ECG Parameters

ECG Parameter	Outside of normal limit if ...	
	Abnormally low	Abnormally high
Heart Rate (bpm)	≤ 50 bpm	≥100 bpm
PR interval (msec)	≤ 120 msec	≥ 200 msec
QRS interval (msec)	≤ 60 msec	≥120 msec
QT interval (msec)	≤ 200 msec	≥500 msec

In addition, the number and percentage of subjects within each of the categories defined below will be presented for the average predose and the maximum postbaseline value during the DB phase by treatment group. The maximum postbaseline value during the double-blind period will be computed for each ECG parameter using data from both scheduled and unscheduled visits.

Categories to assess QT prolongation:

QTc Interval:

- Normal QTc (≤450 msec for male, ≤470 msec for female)
- QTc (>450 to ≤480 msec for male, >470 to ≤480 msec for female)
- QTc (>480 to ≤500 msec)

- QTc (>500 msec)

Clinically significant QTc:

- No (≤ 500 msec)
- Yes (>500 msec)

Change from baseline:

- No concern: QTc ≤ 30 msec
- Concern: QTc $>30 - \leq 60$ msec
- Clear concern: QTc >60 msec

The interpretation of the ECGs as determined by the central reader will be displayed by the number of subjects and percentages meeting the normality criteria. The interpretation will be summarized over time.

Listings of treatment-emergent abnormal ECG values, QTc intervals >450 msec for male and QTc intervals >470 for female, and QTc interval changes >30 msec will also be provided.

6.5. Other Safety Parameters

6.5.1. Columbia Suicide Severity Rating Scale (C-SSRS)

Emergence of suicidal ideation will be assessed using the C-SSRS. The C-SSRS is a low-burden measure of the spectrum of suicidal ideation and behavior. It is a semi-structured clinician-administered questionnaire designed to solicit the occurrence, severity, and frequency of suicide-related ideation and behaviors during the assessment period.

Using the C-SSRS, potentially suicide-related events will be categorized using the following scores:

Suicidal Ideation (1-5)

- 1: Wish to be Dead
- 2: Non-specific Active Suicidal Thoughts
- 3: Active Suicidal Ideation with Any Methods (Not Plan) without Intent to Act
- 4: Active Suicidal Ideation with Some Intent to Act, without Specific Plan
- 5: Active Suicidal Ideation with Specific Plan and Intent

Suicidal Behavior (6-10)

- 6: Preparatory Acts or Behavior
- 7: Aborted Attempt
- 8: Interrupted Attempt
- 9: Actual Attempt (non-fatal)
- 10: Completed Suicide (only applicable for post baseline)

If no events qualify for a score of 1 to 10, a score of 0 will be assigned (0="no event that can be assessed on the basis of C-SSRS"). Higher scores indicate greater severity.

A frequency distribution at each time point by treatment group will be provided. Shifts from baseline to the maximum postbaseline score during the double-blind phase will be summarized by treatment group.

The maximum postbaseline score during the double-blind phase assigned for each subject will be summarized into one of three broad categories: No suicidal ideation or behavior (0), Suicidal ideation (1-5), Suicidal behavior (6-10). Shifts from baseline to the maximum category during the double-blind phase will be summarized by treatment group.

In addition, a frequency distribution at each time point for whether the “subject has engaged in non-suicidal self-injurious behavior” will be presented by treatment group.

A listing of C-SSRS items throughout the study for subjects with Suicidal Ideation or Behavior at any time point will be provided.

6.5.2. Arizona Sexual Experiences Scale (ASEX)

Effect on sexual functioning will be assessed using the ASEX at Baseline, Week 12, and Week 24. The ASEX is a five-item rating scale that quantifies sex drive, arousal, vaginal lubrication/penile erection, ability to reach orgasm, and satisfaction from orgasm. Each of the 5 items is rated on a 6-point Likert scale, ranging from 1 to 6. The 5 items are summed to create a total score, ranging from 5 to 30, with the higher scores indicating more sexual dysfunction. If any item of the scale is missing at a visit, the total score for that scale at that visit will be left blank.

For each of the 5 items, a frequency distribution will be provided by treatment group and gender at each time point. In addition, for each of the 5 items, a frequency distribution will be provided by treatment group, combining the responses for the genders. For this analysis, “vaginal lubrication/penile erection” will be summarized as 1 question. The ASEX total score at each time point and the change from baseline will be summarized with descriptive statistics by treatment group.

The number and percentage of subjects who have ASEX total score 19 or greater, or a score of 5 or greater on any item, or a score of 4 or greater on any 3 items, reflecting sexual dysfunction, will be summarized at each time point by treatment group.

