#### 1.4. Overall Risk and Benefit Assessment

As further described in Section 1 and the rationale for this study (Section 1.3), MDD is a common, serious, recurrent mental disorder. MDD is the leading cause of disability, and its prevalence is rising.

Current therapies commonly used as first-line ADT in patients with MDD (eg, SSRIs and SNRIs) are sub-optimally effective in some patients who require adjunctive treatment, or who are otherwise poorly compliant because of their associated AEs, such as weight gain and sexual side effects. Currently approved adjunctive treatments are limited to the atypical antipsychotic drug class, which present considerable tolerability concerns (eg, metabolic syndrome, akathisia, and EPS). The orexin-receptor antagonist class offers a novel mechanism of action that may prove to be a valuable alternative in the adjunctive treatment of MDD, but without the side effects observed with other medications commonly used in this setting, such as weight gain, sexual side effects, akathisia, or EPS. CCI

The currently available data (see Section 1.1.2, Clinical Studies, and the JNJ-42847922 Investigator's Brochure) support this clinical study that investigates the efficacy and safety of JNJ-42847922 in adult subjects with MDD who have responded inadequately to commonly used first-line ADTs.

The antidepressant effect of JNJ-42847922 was clinically relevant as early as Day 11 of exposure and was sustained at least 14 days after treatment discontinuation. The effect of JNJ-42847922 was largely related to an effect on the core symptoms of depression, and overall unrelated to its effect on sleep-related events.

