## 3. STUDY DESIGN AND RATIONALE

### 3.1. Overview of Study Design

This is a multicenter, randomized, double-blind, active-controlled, parallel-group, flexible-dose, 6-month (24-week) study in adult subjects with MDD who have an inadequate response to current antidepressant therapy with an SSRI/SNRI.

The study will consist of 3 phases: an up to 4-week screening phase, a 6-month double-blind treatment phase, and a 2-week follow-up phase culminating in a follow-up/end-of-study visit. Approximately 100 subjects will be randomized in a 1:1 ratio to receive either flexibly dosed JNJ-42847922 (20 or 40 mg) or flexibly dosed quetiapine XR (150 or 300 mg) as adjunctive therapy to their current SSRI or SNRI. A diagram of the study design is presented in [Figure 1](#) below.

Figure 1: Study Design Schematic

Subjects will continue to take their baseline SSRI/SNRI antidepressant (at the same dose, without change, every day and at approximately the same time as prior to entering the study) throughout the screening, double-blind, and follow-up phases.

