  - 4.2. Be receiving monotherapy treatment for depressive symptoms with one of the following SSRI/SNRI antidepressants, in any formulation: citalopram, duloxetine, escitalopram, fluvoxamine, fluoxetine, milnacipran, levomilnacipran, paroxetine, sertraline, venlafaxine, desvenlafaxine, vilazodone, or vortioxetine at a stable dose (at or above the minimum therapeutic dose level) for at least 4 weeks, and for no greater than 12 months, at screening. Modification of an effective preexisting therapy should not be made for the explicit purpose of entering a subject into the study.
5. Have a MADRS total score  $\geq 25$  (performed by independent, centralized remote raters) at screening and must not demonstrate a clinically significant improvement (ie, an improvement of  $> 20\%$  on their MADRS total score) from the screening to baseline visit.
6. Have a Body Mass Index (BMI) between 18 and 35  $\text{kg/m}^2$  inclusive (BMI =  $\text{weight}/\text{height}^2$ ).
7. Must be otherwise healthy on the basis of physical examination, medical history, vital signs, 12-lead ECG, and clinical laboratory tests performed at screening. If there are abnormalities, they must be consistent with the underlying illness in the study population. If the results of the clinical laboratory tests are outside the normal reference ranges, the subject may be included only if the investigator judges the abnormalities or deviations from normal to be not clinically significant or to be appropriate and reasonable for the population under study. This determination must be recorded in the subject's source documents and initialed by the investigator.
8. Be willing and able to adhere to the prohibitions and restrictions specified in this

protocol.

9. Must sign an informed consent form (ICF) indicating that he or she understands the purpose of and procedures required for the study including peripheral biomarkers research (ie, blood, saliva) and is willing to participate in the study.
10. Sign a separate ICF if he or she agrees to provide an optional DNA sample for research. Refusal to give consent for the optional DNA research sample does not exclude a subject from participation in the study.
11. Criterion deleted per Amendment 2
12. Criterion deleted per Amendment 2
13. A woman must agree not to donate eggs (ova, oocytes) for the purposes of assisted reproduction during the study and for a period of at least 1 month after receiving the last dose of study drug.

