## **Attachment 2: Anticipated Events**

### **Anticipated Event**

An anticipated event is an adverse event (serious or non-serious) that commonly occurs as a consequence of the underlying disease or condition under investigation (disease related) or background regimen.

For the purposes of this study the following events will be considered anticipated events:

- Suicidal thinking, ideation/ behavior,
- Sleep changes/difficulty sleeping, reduced sleep, abnormal sleep, tiredness, fatigue, reduced energy,
- Difficulty in sexual desire, performance or satisfaction,
- Reduced appetite, weight changes (loss or increase),
- Irritability, anger, impulsive behavior,
- Agitation, feeling anxious/anxiety, tension, panic attacks, phobia.

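### The planned ASEX dysfunction rate takes no account of baseline status, so pre-existing cases dilute any drug effect on it

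*SAP*

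**What the plan says.** SAP 6.5.2 schedules the scale at three visits: "Effect on sexual functioning will be assessed using the ASEX at Baseline, Week 12, and Week 24". A subject has dysfunction if the total is 19 or more, any item is 5 or more, or any three items are 4 or more. The number and percentage meeting this, "reflecting sexual dysfunction, will be summarized at each time point by treatment group", is the only planned use of the criterion. The same section has one analysis that refers to baseline: "The ASEX total score at each time point and the change from baseline will be summarized with descriptive statistics by treatment group". Item responses are given as frequency distributions by visit.

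Subjects must have been on a stable SSRI/SNRI "for at least 4 weeks, and for no greater than 12 months, at screening" (Protocol 4.1, criterion 4), and "Subjects will continue to take their baseline SSRI/SNRI antidepressant" throughout (Protocol 3.1). Protocol 1.4 says that some patients on these first-line drugs are "poorly compliant because of their associated AEs, such as weight gain and sexual side effects", and names freedom from sexual side effects among the advantages hoped for from the new class. Protocol Attachment 2 lists "Difficulty in sexual desire, performance or satisfaction" as an anticipated event, defined there as arising from the underlying disease or the background regimen.

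Elsewhere the SAP does use baseline. Orthostatic hypotension is counted for subjects "for whom the orthostatic hypotension was not present at baseline will be tabulated" (SAP 6.3). Laboratory, vital-sign and ECG abnormalities have treatment-emergent rules (SAP 6.2 to 6.4), and C-SSRS has shifts from baseline (SAP 6.5.1).

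**The concern.** The documents themselves give reason to expect subjects who meet the criterion before the first dose. A rate over all subjects at Week 12 or Week 24 adds those who still have the problem to those who developed it on study drug. Only subjects free of dysfunction at baseline can show new onset, so the arm difference in the all-subject rate is smaller than the difference in new onset.

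The study exists to look for features that separate the two drugs, and sexual side effects are among those the protocol names. A diluted measure could make the arms look alike on a feature where they differ. The baseline data needed to do better are already collected.

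**Working it through.** **Inputs.** From SAP 1.4: 50 subjects per arm, 50% discontinuation on quetiapine XR, hazard ratio 0.415, one-sided 0.10. No ASEX rate appears in either document, so every ASEX rate below is an assumption.

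**1. The plan's own figure.** The only design figure is the power for the primary endpoint. Discontinuation on JNJ-42847922 is 1 − 0.5^0.415 = 25.0%. Expected events are 50 × 0.50 + 50 × 0.25 = 37.5. By Schoenfeld's formula, power = Φ(½ × √37.5 × |ln 0.415| − 1.282) = Φ(2.693 − 1.282) = 92.1%, which matches the stated 92%. It says nothing about ASEX. It is used here only for the implied numbers still on drug at Week 24: 25 on quetiapine XR and 37.5 on JNJ-42847922.

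**2. Dilution.** Let b be the proportion with dysfunction at baseline, r the proportion of those who resolve, and i the new-onset rate among the rest. The rate at a visit is b(1 − r) + (1 − b)i. If b and r are the same in both arms, the arm difference is (1 − b) × (difference in i). With r = 0 and new onset of 20% (quetiapine XR) against 10% (JNJ-42847922):

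| b | Quetiapine XR rate | JNJ-42847922 rate | Difference shown |
|---|---|---|---|
| 20% | 36% | 28% | 8 points |
| 30% | 44% | 37% | 7 points |
| 50% | 60% | 55% | 5 points |
| 70% | 76% | 73% | 3 points |

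The true difference in new onset is 10 points in every row. The sign is kept and the size shrinks by 1 − b. A common resolution rate lowers both columns and leaves the difference unchanged. With b from 20% to 70%, r of 0 or 20%, and quetiapine XR onset of 20% or 30%, the share of quetiapine XR cases already present at baseline, b(1 − r) divided by the visit rate, runs from 0.16/0.40 = 40% to 0.70/0.76 = 92%.

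**3. Sensitivity of three summaries.** Assume b = 50%, r = 10%, and onset of 15% (quetiapine XR) against 5% (JNJ-42847922). With 50 per arm:

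- All-subject rate: 0.45 + 0.075 = 52.5% against 0.45 + 0.025 = 47.5%. The difference is 5 points, SE √(2 × 0.2494/50) = 10.0 points.
- Change in rate from baseline: +2.5 against −2.5 points, a difference of 5. The per-subject variances are 0.125 − 0.0006 = 0.1244 and 0.075 − 0.0006 = 0.0744, so SE = √((0.1244 + 0.0744)/50) = 6.3 points.
- New onset among the 25 per arm free at baseline: difference 10 points, SE √((0.1275 + 0.0475)/25) = 8.4 points.

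At Week 24, with 25 and 37.5 subjects (12.5 and 18.75 free at baseline), the SEs become √(0.2494/25 + 0.2494/37.5) = 12.9, √(0.1244/25 + 0.0744/37.5) = 8.3 and √(0.1275/12.5 + 0.0475/18.75) = 11.3 points.

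| Summary | z, no dropout | z, Week 24 |
|---|---|---|
| All-subject rate | 0.5 | 0.4 |
| Change in rate | 0.8 | 0.6 |
| New onset | 1.2 | 0.9 |

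The order is the same in both columns. None reaches 1.28, so at the assumed difference even the new-onset 80% interval would include zero. Expected new cases at Week 24 are 12.5 × 0.15 = 1.9 and 18.75 × 0.05 = 0.9.

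**4. Does the total-score change cover it?** Two of the three routes to the criterion are item-level. A subject scoring 4, 2, 2, 2, 2 (total 12, no dysfunction) who moves to 5, 2, 2, 2, 2 (total 13) becomes a case on a one-point change in total. No item-level change or shift is planned.

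**The case against.** The background drug continues unchanged in both blinded arms, so dysfunction it causes balances in expectation. The arm difference at a visit is still a randomised comparison, and it captures resolution as well as onset. Baseline is one of the tabulated visits, so an imbalance would be visible. The change in total score uses every subject with both scores and depends on no threshold. New sexual complaints reported as adverse events also enter the treatment-emergent tables in SAP 6.1. The measure is descriptive, in an exploratory Phase 2 study, with no test attached.

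Most of this stands, and it rules out a stronger reading. A reader might infer that the planned rate mainly reflects the SSRI/SNRI and not the study drug. The documents do not support that: they give no baseline rate, Attachment 2 names the disease as well as the background regimen, and the effect is diluted, not replaced. Nor would a chance baseline imbalance carry forward in full. Under the step 3 assumptions it would carry at 0.90 − 0.15 = 75% to 0.90 − 0.05 = 85%, and the SE of the all-subject rate already includes it.

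The objection does not make the planned outputs sufficient. Two marginal percentages cannot separate new cases from resolved ones. With dropout as planned, the baseline and Week 24 columns also describe different sets of subjects. Adverse-event reports do not apply the ASEX criterion. It can be said that ESRS-A and PWC in SAP 6.5 have no baseline rule either, but SAP Table 1 shows no baseline for ESRS-A and a single collection for PWC. Of the 6.5 scales with a baseline, C-SSRS has shifts and ASEX does not.

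**Conclusion.** The point holds as a minor one. SAP 6.5.2 does not relate the binary ASEX criterion to baseline status, and pre-existing dysfunction, from the disease or the background antidepressant, dilutes any between-arm drug effect on it by the factor 1 − b. With baseline dysfunction assumed at 20% to 70%, equal in both arms, and no resolution, a 10-point difference in new onset shows as about 8 down to 3 points. These rates are assumptions, so the size of the loss in this trial cannot be fixed from the documents.

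Randomisation protects the planned comparison from bias due to pre-existing dysfunction. What is lost is sensitivity and ease of interpretation. Selective dropout is a separate problem that affects the planned and the added tables alike. Neither the primary result nor the sample size changes.

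**What to change.** Keep the planned rates. Add to SAP 6.5.2, among subjects with both a baseline and a post-baseline ASEX, a shift table of dysfunction (yes/no) by arm at Week 12, Week 24 and End point (DB), all three of which SAP Table 1 already defines for ASEX. From it report:

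- new-onset dysfunction among subjects not meeting the criterion at baseline, with the risk difference and an 80% CI (the level used elsewhere in the SAP), labelled descriptive;
- resolution among subjects meeting the criterion at baseline.

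The cost is one table from data already collected. The downside is a small denominator for new onset. If half the subjects are free of dysfunction at baseline, it is about 25 per arm with no dropout and, at Week 24 under the plan's own discontinuation assumptions, about 12 to 13 on quetiapine XR and 19 on JNJ-42847922. The estimate will be imprecise and should be read beside the all-subject rates and the change in total score.
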